- cost-effective after a time horizon of one year

Study design: TORPEDO-NL will be an investigator-initiated, academically sponsored, multicentre, open-label, randomized controlled trial (RCT) designed to show superiority of CDT (2 systems; technical variant) on top of regular anticoagulation over systemic thrombolysis plus regular anticoagulation in patients with high-risk PE in the Netherlands. A 2:1 (thrombectomy: systemic thrombolysis) randomization will be applied. The randomization procedure will be web-based, using randomly sized blocks consisting of 3,6 or 9 patients. Randomization will occur after the verification that a thrombectomy procedure can be started (randomization-to-needle time) within 60 minutes. Randomization will be stratified by centre.

Study population: Patients with acute PE who are at a high-risk for mortality but do not have 'catastrophic PE' and do not have a strict contraindication to either systemic lysis or CDT, as defined according to the selection criteria, will be enrolled.

Inclusion criteria

- Adult patients with confirmed acute PE, i.e. contrast filling defect in a lobar or more proximal pulmonary artery on computed tomography pulmonary angiography (CTPA), and/or obstructive shock with echocardiographic confirmed dilatation of the right ventricle and a congested vena cava inferior, both with/without echocardiographic signs of clot in transit or deep vein thrombosis of the leg.
- 2. High risk for mortality, i.e.
 - a. post cardiac arrest (after temporary need for cardiopulmonary resuscitation), OR
 - b. obstructive shock (systolic blood pressure <90 mmHg and signs of end-organ hypoperfusion (e.g. elevated lactate levels >2 mmol/l) or the need for vasopressors (adrenalin or noradrenalin) to maintain an adequate blood pressure), OR
 - c. persistent hypotension (systolic blood pressure <90 mmHg or systolic blood pressure drop ≥40 mmHg for at least 15 minutes) not caused by new onset arrhythmia, hypovolemia, or sepsis, OR
 - d. abnormal RV function on transthoracic echocardiography or CTPA AND elevated cardiac troponin levels AND respiratory failure defined as hypoxemia (SaO2 <90%) refractory to O2 supplementation by nasal cannula or Venturi mask, requiring full face mask O2 supplementation (100% FiO2), high-flow nasal O2, or (non-)invasive mechanical ventilation.
- CDT available and technically feasible so as to allow for a randomization-to-needle time of 60 minutes or less.

Exclusion criteria

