3. STUDY DESIGN

TORPEDO-NL will be an investigator-initiated, academically sponsored, multicentre, openlabel, randomized controlled trial (RCT) to show superiority of CDT (2 commercially available systems; technical variant) on top of regular anticoagulation over systemic thrombolysis plus regular anticoagulation in patients with high-risk PE in the Netherlands. A 2:1 (thrombectomy: systemic thrombolysis) randomization will be applied. The randomization procedure will be web-based, using randomly sized blocks consisting of 3,6 or 9 patients. Randomization will occur after the verification that a thrombectomy procedure can be started (randomisation-toneedle time) within 60 minutes. Randomization will be stratified by centre. Patients will be followed for 1 year after randomisation. The primary outcome will be assessed after a 30-day follow-up period (**Figure 1**). The inclusion is estimated to take 2.5 years. Finally, all primary study outcomes will be adjudicated, blinded, by an independent critical events committee, a more detailed description will be provided in paragraph 8.1.1.

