8. METHODS

8.1 Study parameters/endpoints

8.1.1 Main study endpoint

The primary outcome is the composite incidence of the binary endpoints of all-cause mortality, treatment failure, major bleeding and all-cause stroke at day 30.

Treatment failure in the first six hours after randomization is defined as life-threatening hemodynamic or respiratory deterioration. This deterioration is the clinical scenario if, following randomisation, the patient develops overt cardiorespiratory instability over at least 15 minutes necessitating CPR, escalation of respiratory support, or ECMO. After these first six hours, treatment failure will also be defined by increasing dosages of cardiorespiratory support (e.g. oxygen, catecholamines), and lack of improvement. Lack of improvement is defined by the presence of at least one of the following criteria: i) an equal or rising SCAI SHOCK stage (**Table 1**), ii) an equal or rising Fraction of Inspired Oxygen (FiO₂) level to maintain adequate oxygen saturation (i.e. \geq 92%), or iii) an equal or decreasing P/F ratio. Treatment failure will be determined every 6 hours starting at the moment of randomisation, until the patient is considered stable and transferable to the ward.

Upon establishing the outcome 'treatment failure' physicians are allowed to escalate therapy in whatever way they consider appropriate. Therapy crossover without meeting the primary outcome is not allowed. Major bleeding is defined as Bleeding Academic Research Consortium (BARC)3b and BARC3c bleeding (=intracranial haemorrhage).²¹ Ischemic stroke is defined as any stroke (National Institutes of Health Stroke Scale \geq 1).

All primary study outcomes will be adjudicated by an independent critical events committee. This committee will consist of an independent group of three individuals with pertinent expertise that reviews and adjudicates important endpoints and relevant AEs reported by study investigators. The committee will be blinded to treatment assignment and review safety event dossiers, which may include copies of subject source documents provided by study sites, for all reported cases where the primary outcome was met. Committee members may include (interventional) cardiologists, intensivists, pulmonologists, vascular medicine specialists, and (interventional) radiologists, as well as other experts with the necessary therapeutic and subject matter expertise to adjudicate the event categories outlined above.

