8.3 Study procedures

The study starts as soon as the patients is identified as eligible for inclusion and randomised. All patients, i.e. both study arms, will be treated with an UFH bolus after diagnosis. Patients randomised to the usual care arm will be treated with UFH or LMWH with systemic thrombolysis. Patient randomised to the intervention will be treated with UFH or LMWH (see paragraph 5.2 for specifics) and transferred to the cath lab and subjected to the thrombectomy. All further diagnostic tests (e.g. echocardiography, repeated blood test) are used along clinically relevant but not dictated by this protocol. No biomarkers or imaging test at baseline or follow-up will be required for the study. The SCAI SHOCK stage will be assessed at baseline and every 6 hours starting from randomization until the patient is stabilized and transferable to a normal ward (**Table 1**).^{26,27} At 48 hours following randomisation, the amount of oxygen supplementation (I O_2 /min) is noted in the medical chart. Patients will be contacted by the Sponsor on day 7 (± 2 days), at 3 months (± 1 week), at 6 months (± 1 week), at 9 months (± 1 week) and at 12 months (± 2 weeks) by e-mail to complete the PROMS questionnaire(s) (**Table 2**).

Stage	Α	В	С	D	E
Condition	Hemodynamically	Hemodynamically	Hypoperfusion	Failure to	Extremis /
	stable	unstable	= Shock	stabilize with	refractory shock
				initial therapy	
Hypotension:					
- SBP	>90 mm Hg	60-90 mm Hg	60-90 mm Hg	60-90 mm Hg	<60 mm Hg
- MAP	>65 mm Hg	50-65 mm Hg	50-65 mm Hg	50-65 mm Hg	<50 mm Hg
		OR	AND	AND	OR
Hypoperfusion					
- Arterial lac-					
tate	<2 mmol/L	2-5 mmol/L OR	2-5 mmol/L O R	>5-10 mmol/L	>10 mmol/L
			200-500 U/L	OR	OR
- ALAT	<200 U/L	200-500 U/L	≥ 7.2	>500 U/L	< 7.2
- рН	≥ 7.2	≥ 7.2		≥7.2	
		AND	AND	OR	OR
Treatment	No Drugs	No Drugs	No Drugs	2 Drugs	≥3 Drugs OR
intensity	No Devices	No Devices	No Devices		Device
			OR	OR	OR
			1 Drug without	1 Drug with	Out-of- or in-
			hypotension or	persistent	hospital cardiac
			hypoperfusion	hypotension or	arrest
				hypoperfusion	

Table 1: SCAI SHOCK stage overview. SBP = systolic blood pressure; MAP = mean arterial pressure; ALAT = alanine aminotransferase, Drugs = intravenous vaso-active drugs, Devices = RV support or VA-ECMO; hypotension = SBP ≤90 mm Hg or MAP ≤65 mm Hg

	7 Days	3 Months	6 Months	9 Months	1 Year
EQ-5D-5L	Х	Х	Х	Х	Х
ICHOM-VTE -	Х	Х	Х	Х	Х

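### Blinded adjudication starts from unblinded site reports, so it can correct over-called events but cannot reliably recover under-called ones, chiefly treatment failures

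*Protocol*

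**What the plan says.** The Protocol describes a "multicentre, open-label, randomized controlled trial (RCT") with 2:1 allocation to CDT. Section 3 promises that "all primary study outcomes will be adjudicated, blinded, by an independent critical events committee", and section 8.1.1 repeats the commitment.

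Section 8.1.1 then fixes how cases arrive. The three-member committee "reviews and adjudicates important endpoints and relevant AEs reported by study investigators". On blinding and material it says: "The committee will be blinded to treatment assignment and review safety event dossiers, which may include copies of subject source documents provided by study sites". That review is "for all reported cases where the primary outcome was met".

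For the component most open to judgement, section 8.1.1 states: "Treatment failure will be determined every 6 hours starting at the moment of randomisation, until the patient is considered stable and transferable to the ward". Section 8.3 adds: "The SCAI SHOCK stage will be assessed at baseline and every 6 hours starting from randomization". Neither section says that these records go to the committee for patients whom the site regards as event-free.

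**The concern.** Two decisions come before any blinded reading: that something is reported, and that the primary outcome has been met. Site staff who know the allocation make both. Parts of the treatment-failure definition need bedside judgement, such as overt instability, the need to escalate respiratory support, and the point at which a patient counts as stable and assessment stops.

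A failure that the site does not call has no stated route to the committee. If such omissions are more common in the CDT arm, the observed CDT rate falls and a benefit can appear where none exists. A later analysis cannot repair this, because the missed events were never put before a blinded reader. Blinded adjudication is the safeguard that the Protocol names for outcome assessment in an open-label design, so its reach matters.

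**Working it through.** **1. The plan's own figures.** Section 4.4 assumes 0.19 (CDT) against 0.46 (systemic thrombolysis), with a difference of 27.5 points and an OR of 3.71. The last two figures imply a control rate of 0.465. Exact two-sided Fisher power at 35/70 is 79.1% for 0.46 and 80.5% for 0.465, against the stated 80%. Drop-out inflation gives 35/0.95 = 36.8, so 37, and 70/0.95 = 73.7, so 74, for a total of 111. The sample size reproduces and is not in dispute.

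**2. Routes to the blinded committee, as written.**
- Site reports the primary outcome as met: dossier reviewed (8.1.1).
- Site reports a relevant adverse event below the threshold: adjudication is mentioned (8.1.1), but the dossier sentence covers only outcome-met cases. The two are not reconciled.
- Site makes no call: no route stated. Monitors check the CRF against source documents (12.2), but no referral to the committee is described.

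**3. How much of the effect is exposed.** Section 4.4 splits the 27.5 points into 5 (mortality), 21.5 (treatment failure or major bleeding) and 1 (ischaemic stroke). 21.5/27.5 = 78%.

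**4. How many patients would have an outcome dossier.** 0.19 × 74 + 0.465 × 37 = 14.1 + 17.2 = 31.3 expected events. About 31 patients would have a dossier and about 80 of 111 would not.

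**5. Illustration of size.** Let p be the true event rate in both arms (no effect), d the death rate (always captured), and m the share of non-fatal CDT events never reported. The thrombolysis arm is observed at p and the CDT arm at

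p_obs = d + (p − d)(1 − m).

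All 2×2 tables at 37/74 were enumerated with binomial probabilities. The test is the unadjusted logistic Wald test, in line with section 10.1: z = ln(OR) / √(sum of reciprocal cell counts), rejecting when |z| > 1.96. The values of p, d, m and the one-arm direction are assumptions.

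Example: p = 0.40, d = 0.10, m = 0.20 gives p_obs = 0.10 + 0.30 × 0.80 = 0.34.

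| p | m | d = 5% | d = 10% | d = 15% |
|---|---|---|---|---|
| 0.40 | 0 | 4.8% | 4.8% | 4.8% |
| 0.40 | 10% | 6.4% | 6.0% | 5.6% |
| 0.40 | 20% | 11.3% | 9.5% | 8.1% |
| 0.40 | 30% | 19.9% | 15.7% | 12.3% |
| 0.19 | 0 | 3.9% | 3.9% | 3.9% |
| 0.19 | 20% | 6.0% | 4.9% | 4.2% |
| 0.19 | 30% | 8.3% | 5.9% | 4.4% |

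At p = 0.46, the planned control rate, the ranges are 9.6-13.2% (m = 20%) and 15.6-24.1% (m = 30%), from about 5% at m = 0. In the worked example, 9.1 of the 9.5 points are false findings in favour of CDT. If the same share is missed in both arms at p = 0.40, the error stays at about 4.5-4.7%.

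**The case against.** - **Blinding still does useful work.** Section 8.1.1 bars crossover until the primary outcome is met, so a clinician who wants to escalate has a reason to call treatment failure. Blinded review can overturn such a call. A reader might infer that blinding gives the primary endpoint no protection. The documents do not support that: the protection is one-sided. This stands.
- **Some missed events could be restored.** Reported adverse events also go to the committee, so a bleed or neurological event that the site graded too low could be upgraded. It would be too strong to say that the committee can only delete events. The route still needs a site report, and it does little for a treatment failure that nobody called.
- **The definition is partly objective.** CPR and ECMO are hard facts. After six hours the criteria use SCAI stage, FiO2, P/F ratio and level of support at fixed intervals, which limits silent omission. It does not remove it, because the site still applies the definition.
- **Deaths can hardly go unreported.** If any CDT event could be missed, deaths included, the 40% case would give 13.3% and 24.8%. Those figures overstate the exposure and are not used here.
- **One-sided under-reporting is hypothetical.** The documents give neither a rate nor a direction. This stands, and it is why the table is only an illustration.
- **A committee charter might add triggers.** None is cited for this committee, and the Protocol's own sentence on dossiers points the other way.

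**Conclusion.** The point holds in a limited form. As written, dossier review covers cases that unblinded sites report as having met the primary outcome. It can correct over-calling, but it cannot reliably correct under-calling of the non-fatal components: chiefly treatment failure, then bleeding grade and mild stroke. Mortality is hardly exposed.

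The size depends on assumptions that the documents cannot settle. With under-reporting confined to CDT and a true rate near 40%, the inflation is material: roughly 8-11% at 20% missed and 12-20% at 30% missed, against 4.8%. Near a 19% rate it is small, at about 4-6% and 4-8% against 3.9%. With equal under-reporting there is none. The Protocol does not show that such bias will occur. It shows that the stated procedure would not detect it. This should be changed because the change is cheap and the gap lies in the primary endpoint.

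**What to change.** Amend section 8.1.1 so that the existing blinded committee applies the endpoint definition, whatever the site's own call, to redacted standard dossiers of either:

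- all 111 randomised patients, or
- every case flagged by program from data held on all patients: the six-hourly SCAI stage and treatment-failure assessments, CPR, ECMO, and reported bleeding and neurological adverse events.

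Report disagreements between site and committee by arm and by direction. Bring the sentence on reported adverse events and the sentence on dossiers into line.

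Sample size, treatment and endpoint definition do not change. The costs are a listing program and more committee time. An unchanged SCAI stage, FiO2 or P/F ratio counts as lack of improvement, so triggers on single fields could flag close to all 111 patients, and reviewing everyone may be simpler. The eCRF must hold the six-hourly FiO2, P/F and support values. Sites already need these to determine treatment failure, but section 8.3 names only SCAI stage at that interval, so their capture has to be confirmed or added.

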8.2 Randomization, blinding and treatment allocation

A 2 (CDT: systemic thrombolysis) :1 (TT) randomisation will be applied. The randomization procedure will be web-based (castor), using randomly sized blocks consisting of 3,6 or 9 patients. Randomization will occur after the verification that a thrombectomy procedure can be started (randomisation-to-needle time) within 60 minutes. Randomization will be stratified by centre.

8.3 Study procedures

The study starts as soon as the patients is identified as eligible for inclusion and randomised. All patients, i.e. both study arms, will be treated with an UFH bolus after diagnosis. Patients randomised to the usual care arm will be treated with UFH or LMWH with systemic thrombolysis. Patient randomised to the intervention will be treated with UFH or LMWH (see paragraph 5.2 for specifics) and transferred to the cath lab and subjected to the thrombectomy. All further diagnostic tests (e.g. echocardiography, repeated blood test) are used along clinically relevant but not dictated by this protocol. No biomarkers or imaging test at baseline or follow-up will be required for the study. The SCAI SHOCK stage will be assessed at baseline and every 6 hours starting from randomization until the patient is stabilized and transferable to a normal ward (**Table 1**).^{26,27} At 48 hours following randomisation, the amount of oxygen supplementation (I O_2 /min) is noted in the medical chart. Patients will be contacted by the Sponsor on day 7 (± 2 days), at 3 months (± 1 week), at 6 months (± 1 week), at 9 months (± 1 week) and at 12 months (± 2 weeks) by e-mail to complete the PROMS questionnaire(s) (**Table 2**).

Stage	Α	В	С	D	E
Condition	Hemodynamically	Hemodynamically	Hypoperfusion	Failure to	Extremis /
	stable	unstable	= Shock	stabilize with	refractory shock
				initial therapy	
Hypotension:					
- SBP	>90 mm Hg	60-90 mm Hg	60-90 mm Hg	60-90 mm Hg	<60 mm Hg
- MAP	>65 mm Hg	50-65 mm Hg	50-65 mm Hg	50-65 mm Hg	<50 mm Hg
		OR	AND	AND	OR
Hypoperfusion					
- Arterial lac-					
tate	<2 mmol/L	2-5 mmol/L OR	2-5 mmol/L O R	>5-10 mmol/L	>10 mmol/L
			200-500 U/L	OR	OR
- ALAT	<200 U/L	200-500 U/L	≥ 7.2	>500 U/L	< 7.2
- рН	≥ 7.2	≥ 7.2		≥7.2	
		AND	AND	OR	OR
Treatment	No Drugs	No Drugs	No Drugs	2 Drugs	≥3 Drugs OR
intensity	No Devices	No Devices	No Devices		Device
			OR	OR	OR
			1 Drug without	1 Drug with	Out-of- or in-
			hypotension or	persistent	hospital cardiac
			hypoperfusion	hypotension or	arrest
				hypoperfusion	

Table 1: SCAI SHOCK stage overview. SBP = systolic blood pressure; MAP = mean arterial pressure; ALAT = alanine aminotransferase, Drugs = intravenous vaso-active drugs, Devices = RV support or VA-ECMO; hypotension = SBP ≤90 mm Hg or MAP ≤65 mm Hg

	7 Days	3 Months	6 Months	9 Months	1 Year
EQ-5D-5L	Х	Х	Х	Х	Х
ICHOM-VTE -	Х	Х	Х	Х	Х
Core set –					
Individual					
Questions					
(Satisfaction					
with treatment					
/ Changes in					
life view)					
PEMB-QoL 40	Х	Х	Х	Х	Х
items					
PROMIS GH	Х	Х	Х	Х	Х
ten items					
PROMIS	Х	Х	Х	Х	Х
Numeric Rating					
Scale v1.0 -					
Pain Intensity					
1a_DUT_FLE					
PROMIS SF	Х	Х	Х	Х	Х
v1.0 - Dyspnea					
Severity short					
form 10a					
PVFS scale one	Х	Х	Х	Х	Х
item					

Table 2: Questionnaire overview. The y-axis represents the type of questionnaire, while the x-axis indicates the time points at which the patient receives the questionnaires.

8.4 Withdrawal of individual subjects

Subjects can leave the study at any time for any reason if they wish to do so without any consequences. The investigator can decide to withdraw a subject from the study for urgent medical reasons.

8.5 Replacement of individual subjects after withdrawal

The study will be continued until 111 patients have been randomized and completed the first 30 days of follow-up (or met the primary outcome within that period).

8.6 Follow-up of subjects withdrawn from treatment

The primary outcome will be assessed following the principles of intention to treat (ITT). Hence, if the reperfusion treatment to which the patient is allocated to receive is not provided, the patient will still be followed for the occurrence of primary and secondary outcomes.

8.7 Premature termination of the study

The study will be prematurely terminated if recommended by the DSMB for safety reasons in the intervention arm. The DSMB charter of the trial explains the specific discontinuation criteria.

9. SAFETY REPORTING

9.1 Temporary halt for reasons of subject safety

In accordance to section 10, subsection 4, of the WMO, the sponsor will suspend the study if there is sufficient ground that continuation of the study will jeopardise subject health or safety. The sponsor will notify the accredited METC without undue delay of a temporary halt including the reason for such an action. The study will be suspended pending a further positive decision by the accredited METC. The investigator will take care that all subjects are kept informed.

9.2 AEs, SAEs and SUSARs

9.2.1 Adverse events (AEs)

Adverse events are defined as any undesirable experience occurring to a subject during the study, whether or not considered related to the study intervention. All adverse events reported spontaneously by the subject or observed by the investigator or his staff will be recorded. Only adverse events related to the study (i.e. as a consequence of the reperfusion therapy the patient is randomized to, e.g. bleeding and per procedure complications) will be reported to the METC, as no patient benefit is expected from reporting non-study related adverse events.

9.2.2 Serious adverse events (SAEs)

A serious adverse event is any untoward medical occurrence or effect that

- results in death;
- is life threatening (at the time of the event);
- requires hospitalisation or prolongation of existing inpatients' hospitalisation;
- results in persistent or significant disability or incapacity;
- is a congenital anomaly or birth defect; or
- any other important medical event that did not result in any of the outcomes listed above due to medical or surgical intervention but could have been based upon appropriate judgement by the investigator.

An elective hospital admission will not be considered as a serious adverse event.

The lead investigator (or his/hers representative) of each participating site will report all SAEs related to participation in this study protocol to the lead investigator of the LUMC. Since the patients under study are expected to be at high risk for developing SAEs, we would like to Version 2.1: 16-12-2024 27 of 38

suggest line-listing every 6 months for reporting SAEs. The main reason for line-listing applies to the feasibility of reporting the SAEs besides all other study activities, which is expected to be of burden for the accredited METC. If there is an SAE that is thought to be in direct relation with the safety of the study we will follow the usual regulations of reporting SAEs. The lead investigator of the LUMC will report all SAEs related to participation in this study protocol to the sponsor without undue delay after obtaining knowledge of the events. The sponsor will report the SAEs related to participation in this study protocol through the web portal ToetsingOnline to the accredited METC that approved the protocol, within 7 days of first knowledge for SAEs related to participation in this study protocol that result in death or are life threatening followed by a period of maximum of 8 days to complete the initial preliminary report.

SAEs that are considered study specific include:

- Laceration of a blood vessel
- Haemothorax
- Cardiac tamponade
- Damage to the heart valve
- Pneumothorax

